#### **Infections**

Summaries of infections will be based on treatment period and follow-up period pooled together by each grade and will be provided for grade 3, 4 and 5, respectively, as well as all infections regardless of grades.

In addition, the following summaries will be presented:

- 1) Summary of worst-grade infections by Binet stage and Rai stage and by neutrophil grade at baseline.
- 2) Summary of type of infections by all infections, all respiratory tract infections, lower respiratory tract infections, upper respiratory tract infections, sepsis and other infections.
- 3) Summary for drug-related infections
- 4) Summary of infections for subjects with baseline neutropenia.

### **Mucocutaneous Reactions**

An overview of mucocutaneous reactions and a summary of will be provided.

A summary of all mucocutaneous reactions and all serious mucocutaneous reactions within 60 days after the last ofatumumab dose will also be provided.

A subject listing of all mucocutaneous reactions will be provided

### **AEs Associated with Decreased neutrophil count/hemoglobin count/platelet count**

A summary of AEs associated with decreased neutrophil count; a summary of AEs associated with decreased hemoglobin count; a summary of AEs associated with decreased platelet count; and a summary of AEs associated with other cytopenias will be provided.

In addition, mucocutaneous reactions reported as adverse events will be summarized and listed separately.

### **Prolonged and late-onset neutropenia**

Prolonged neutropenia is defined as Grade 3/4 neutropenia that occurred during the treatment period and was not resolved at least 42 days post the last dosing date.

Late-onset neutropenia is defined as Grade 3/4 neutropenia starting at least 42 days after the last treatment dose.

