3.1.4. Follow-up Phase

Survival and disease status assessments (physical examination and evaluation of peripheral blood samples) will be performed post treatment every 3 months for 5 years after last treatment.

A bone marrow examination is required to confirm Complete Remission (CR) at least 2 months after completion of therapy and when a subject fulfills the International Workshop for Chronic Lymphocytic Leukemia (IWCLL) updated National Cancer Institute-Sponsored Working Group (NCI-WG) requirements for Complete Remission (CR) [Hallek, 2008]. Previous results may be used or if not available, a bone marrow exam may be done at screening. If a subject's response improves to a CR while on study, then a bone marrow examination is required to confirm CR at least 2 months after response as per the updated IWCLL NCI-WG requirements for CR [Hallek, 2008].

Additionally, CT Scans are required yearly while on study, including during follow-up, and at disease progression, whenever that may occur.

Subjects demonstrating disease progression will be followed for survival status until study completion. Follow-up assessment after disease progression on treatment will assess survival status, date of next CLL therapy, type of therapy and response to therapy. It is acceptable for the information for survival follow-up visits to be collected remotely (via telephone, email), as necessary. The frequency of the survival follow-up visits should be per local standard of care, suggested every 3 months for CLL. Minimally, this should be collected at least annually.

PRO measures (EORTC QLQ-C30, EORTC QLQ-CLL16, EQ-5D and a Health Change Questionnaire) will be administered for completion by the subject at follow-up visits, as per Section 6.5.6.

Please refer to Section 6: Study Assessments and Procedures for detailed assessment instructions.

Supplementary study conduct information not mandated to be present in this protocol is provided in the accompanying Study Procedures Manual (SPM). The SPM will provide the site personnel with additional administrative and detailed technical information.

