6.3.2. Peripheral Blood Sampling for Hematology and Biochemistry

Blood samples will be drawn for analysis of the following parameters at visits according to the time and events schedule:

- **Hematology:** hemoglobin, hematocrit, reticulocytes, platelets, leukocytes, and white blood cell differential (neutrophils, eosinophils, basophils, lymphocytes and monocytes, prolymphocytes - all expressed in % and in absolute numbers)
- **Biochemistry:** sodium, potassium, chloride, bicarbonate, calcium, blood urea nitrogen (BUN), creatinine, uric acid, total bilirubin, alkaline phosphatase (ALP), aspartate aminotransferase (AST), alanine aminotransferase (ALT), lactic acid dehydrogenase (LDH), albumin, glucose (random). Haptoglobin will be analyzed at screening and 3 months after last treatment.

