6.4.8. Time Period and Frequency of Detecting AEs and SAEs

All SAEs and AEs regardless of relationship to investigational product will be collected from the first dose of investigational product to 60 days after the last dose of investigational product and will be documented on the eCRF. All SAEs and AEs for subjects not receiving treatment (observation) will be collected for the same duration of time (i.e. Visit 1 until 60 days after last visit, up Visit 14). Only SAEs will be reported from 60 days after the last dose of investigational product or last treatment/observation

visit to the end of the follow-up period. All SAEs regardless of causality will be collected until the end of the follow-up period.

Subject who are HBsAg negative, anti-HBc positive and HBV DNA negative may be included in the study but must undergo HBV DNA monitoring. Consult with a physician experienced in care and management of subjects with hepatitis B to manage/treat subjects who are anti-HBc positive. Anti-viral therapy should be initiated, if required. If a subject's HBV DNA becomes positive during the study, the Novartis medical lead should be notified. The risks and benefits of continuing ofatumumab or discontinuing ofatumumab should be discussed with the medical lead before appropriate treatment decisions are made for that individual subject.

From the time a subject consents to participate in and completes the study (See Section 4.4), all SAEs assessed **as related to study participation** (e.g., protocol-mandated procedures, invasive tests, or change in existing therapy) will be reported promptly to Novartis.

Any pre-existing condition or signs and symptoms present prior to investigational product will be recorded as medical history.

Any SAE brought to the investigator's attention after the subject has completed the study and considered by the investigator as possibly related to investigational product must be reported to Novartis.

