11. APPENDICES

11.1. Appendix 1: Time and Events

Phase	SCREEN	Treatment or Observation (~ every 8 wks after 1 st visit)			Follow-up (every 3 months for 5 years)	WD
		1	2	3-14		
Visit	Screening	1	2	3-14	15-34	
Week	(-6 to -1)	1	2	9-97	109-337	
Month	0	1	1	3-25	28-85	
Visit Window		± 7d	± 3d	± 7d	± 14d	
Administration of Ofatumumab (if assigned to treatment group)		X	X	X		
Informed Consent	X					
Eligibility Criteria	X					
Demographics	X					
Medical History ¹	X					
Height	X					
Body weight	X		X	X	X	X
Physical Exam	X		X	X	X	X
Lymph node evaluation	X		X	X	X	X
Organ Evaluation	X		X	X	X	X
ECOG	X		X	X	X	X
ECG	X					
Adverse Event Assessments		X	X	X	X ¹²	X
Concomitant Medications		X	X	X	X ¹²	X
CT Scan	X			X ²	X ²	X
Bone marrow biopsy	X ³			X ³		
Flow cytometry (MRD)	X ³			X ³	X ³	X ³
Flow cytometry(CD5/CD19)	X			X	X ⁴	X
Prognostic Factors ⁵	X					X
Response Evaluation		X	X	X	X	X
PRO	X			X	X	X
Hematology ⁶	X	X	X	X	X	X
Biochemistry ⁶	X	X	X	X	X	X
Hepatitis ⁷ and Pregnancy Test	X					
Igs	X			X ^{8,9}		
HABA ¹⁰		X		X ^{8,9}	X ⁹	X
Coombs and CH50	X				X	
PK Sampling ¹¹		X	X	X	X	X
Vital Signs	X	X	X	X	X	

1. Medical history to include disease characteristics as defined in Section 6.1.
2. Screening, yearly while on study, at the subject's last treatment visit and upon relapse
3. For subjects in CR ONLY- may be confirmed with bone marrow biopsy/flow cytometry
4. Until B-cell value is within normal levels (See Section 6.3.1.2.)
5. Prognostic Factors as defined in Section 6.3.3
6. See Section 6.3.2
7. Subjects that are HBsAg negative, HBcAb positive and HBV DNA negative may be included but must undergo HBV DNA monitoring as listed in Section 6.3.4
8. At the subject's last treatment visit
9. Every six months. Igs may be assessed during infection per PI. (See Section 6.3.4)
10. HAHA for ofatumumab treatment only-predose, every six months, at last treatment, and 3& 6 months post last ofatumumab dose, regardless of when it occurs.
(See Section 6.3.4)
11. For pharmacokinetic sampling, see Table 5, Section 6.6; + 15 min window for 0.5h post EOI samples is allowed
12. Only SAEs and associated concomitant medications are to be reported from 60 days after the last dose/observation time. (See Section 6.4.8.)

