### **12.2. Adverse Events**

All SAEs and AEs regardless of relationship to investigational product will be collected from the first dose of investigational product to 60 days after the last dose of investigational product and will be documented on the eCRF. All SAEs and AEs for subjects not receiving treatment (observation) will be collected for the same duration time (i.e. Visit 1 until 60 days after last visit, up to Visit 14). Only SAEs will be reported from 60 days after the last dose of investigational product or last treatment/observation visit to

the end of the follow-up period. All SAEs regardless of causality will be collected until the end of the follow-up period.

An overview summary of AEs, including counts and percentages of subjects with any AE, AEs related to study treatment, AEs leading to permanent discontinuation of study treatment, AE leading to dose reductions, AEs leading to dose delays/ interruptions, SAEs, SAEs related to study treatment, fatal SAEs, and fatal SAEs related to study treatment will be produced.

A summary of non-serious AEs that occurred in strictly 5% of the subjects or above will be provided (no rounding for the percentage will be used in terms of 5% threshold, e.g., event with 4.9% incidence rate should not be included in this table). The summary will be displayed by SOC and PT.

The relationship between MedDRA SOC, PT, and Verbatim Text will be displayed.

Adverse events (AEs) will be graded according to the CTCAE, Version 4.0. Adverse events will be coded to the preferred term (PT) level using the Medical Dictionary for Regulatory Affairs (MedDRA dictionary).

A summary of number and percentage of subjects with any adverse events by maximum grade will be produced. AEs will be sorted by Preferred term (PT) in descending order of total incidence. The summary will use the following algorithms for counting the subject:

- **Preferred term row:** Subjects experiencing the same AE preferred term several times with different grades will only be counted once with the maximum grade.
- **Any event row:** Each subject with at least one adverse event will be counted only once at the maximum grade no matter how many events they have.

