### 12.3. Adverse Events of Special Interest

A comprehensive list of MedDRA terms based on clinical review will be used to identify each type of events. Changes to the MedDRA dictionary may occur between the start of the study and the time of reporting and/or emerging data from on-going studies may highlight additional adverse events of special interest, therefore the list of terms to be used for each event of interest and the specific events of interest will be based on the safety review team (SRT) agreements in place at the time of reporting.

The events of special interest include

- Infusion related AEs
- Infections
- Mucocutaneous reactions
- AEs associated with decreased neutrophil, hemoglobin or platelet count
- Prolonged and late-onset neutropenia
- Autoimmune Hematologic Complication Adverse Events
- Tumor Lysis Syndrome (TLS)

Summaries of the number and percentage of subjects with these events will be provided for each type of event separately.

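### Late-onset neutropenia reads as an AE-based count with no end date, although non-serious AEs stop being collected at day 60; it should be derived mainly from laboratory neutrophil counts.

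*SAP*

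**What the plan says.** SAP 12.3 defines the event in one sentence: "Late-onset neutropenia is defined as Grade 3/4 neutropenia starting at least 42 days after the last treatment dose". It gives a start but no end, and does not say what happens once another anti-cancer therapy begins. The opening of SAP 12.3 covers identification: "A comprehensive list of MedDRA terms based on clinical review will be used to identify each type of events". Prolonged and late-onset neutropenia is on the list that follows.

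On collection, Protocol 6.4.8 has all AEs recorded "from the first dose of investigational product to 60 days after the last dose" of product. After that, per footnote 12 of Protocol Appendix 1, "Only SAEs and associated concomitant medications are to be reported from 60 days after the last dose/observation time". SAP 12.2 repeats the rule. Serious events continue: "All SAEs regardless of causality will be collected until the end of the follow-up period".

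On blood counts, Protocol 6.3.2 says "Blood samples will be drawn for analysis of the following parameters at visits according to the time and events schedule", and its haematology panel includes neutrophils. Appendix 1 marks haematology at every treatment, follow-up and withdrawal visit. Protocol 3.1.4 sets follow-up visits every 3 months for 5 years.

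The planned outputs are Table 3.1110 and Listing 23.0410. Both appear in the SAP for the 280-event analysis and again in the SAP for the final analysis.

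**The concern.** The definition looks for an event that begins six weeks or more after the last infusion, but the ordinary means of recording a non-serious event closes 18 days later. A neutrophil count of, say, 700/µL in a well subject at the 3-month visit meets the grade 3 criterion in Protocol Table 4. If it is not serious, it creates no AE record and so would not enter an AE-based late-onset table. Protocol 6.4.1.2 equates about 5 months with about 5 half-lives, so drug exposure continues well past day 60 and these are the months the definition is meant to cover.

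The bias can also run the other way. With no stop at next therapy, a serious neutropenia during later chemotherapy would be counted as late-onset after ofatumumab. The sponsor recognised this issue for SAEs generally by adding Table 3.0929, which separates events before and after next therapy. The late-onset definition was not changed to match.

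**Working it through.** **1. Source.** MedDRA terms attach to AE records, not to laboratory values. Where SAP 12.3 wants a laboratory derivation it says so: tumour lysis syndrome has its own laboratory criteria table. The neutropenia definition has nothing comparable. Programmatic grading of laboratory values is in SAP 12.7 and is not linked to this event. The AE reading is therefore the more literal one.

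**2. Visit calendar (Protocol Appendix 1).** Visits 3–14 at 8-week steps: 9 + 8 × 11 = Week 97. Visits 15–34 at 12-week steps: 109 + 12 × 19 = Week 337. Both match the printed ranges.

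**3. First follow-up count after the last planned dose.**
- (109 − 97) × 7 = day 84; with the ±14-day window, days 70 to 98.
- Reading 3 months as about 91 days: days 77 to 105.
- If the Week 97 dose is also 7 days late, at the limit of its ±7-day window: 84 − 14 − 7 = day 63.

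All of these are after day 60.

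**4. Full AE collection inside the late-onset window.** 60 − 42 = 18 days (19 counted inclusively). Scheduled counts in those days for a completer: 0. Scheduled counts at day 42 or later: up to 20, from day 84 to (337 − 97) × 7 = day 1680. Twenty is a ceiling, because after progression subjects move to survival follow-up, which may be remote (Protocol 3.1.4).

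**5. Subjects who stop early.** Someone who attends the next 8-weekly visit but is not dosed has haematology at 8 × 7 = day 56 ± 7, that is days 49 to 63, mostly inside the window. A withdrawal visit also carries haematology, and Protocol 6.3 allows unscheduled counts. On the other side, Protocol 4.4 puts subjects who stop product on the follow-up schedule, which is 3-monthly. So some, not all, will have a count in days 42–60.

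**6. What 3-monthly sampling can detect.** The documents give no episode length, so it is assumed here. For one episode of D days placed at random against counts every 84 days, the chance that a count falls in it is min(1, D/84):

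| Assumed D (days) | Chance of a count |
|---|---|
| 14 | 14/84 = 17% |
| 28 | 28/84 = 33% |
| 42 | 42/84 = 50% |
| 84 or more | 100% |

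A laboratory derivation would be incomplete for short episodes but would detect longer ones well.

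**The case against.** The strongest reply is that an AE-only source is inferred. The definition speaks of grade 3/4 neutropenia without mentioning AE reports. Tumour lysis syndrome is on the same list and is calculated from laboratory data. Table 3.1110 sits among laboratory displays, away from the AE neutrophil tables (3.0760 to 3.0780), and its title lacks their AE wording. SAP 9.2 also defers derivations to separate dataset specifications, which are not among the documents. This stands to the extent that the source is open to dispute. It does not remove the point: the only identification rule stated for this event is the MedDRA one, and two competent programmers could produce different tables.

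A second reply is that the laboratory data are shown elsewhere: graded haematology in Tables 3.1040 and 3.1050, and a laboratory-versus-AE comparison for neutrophils in Listing 23.0420. That is correct, and it limits the harm. A low count at month 3 would not vanish from the report; it would be missing from the display named for it.

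A reader might go further and infer that the late-onset rate is close to zero by construction, or that only about 1% of the event is captured, since 18/(1680 − 42) = 1.1%. The documents support neither. Serious cases are collected throughout, some early stoppers have counts in the window, and a share of calendar time is not a share of cases.

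**Conclusion.** The point holds as an under-count, conditional on SAP 12.3 being applied as written. Under that reading, non-serious grade 3/4 neutropenia starting after day 60 is omitted. For completers, no scheduled count falls in the 18 days when non-serious events could still be reported. The number of cases lost cannot be estimated from the documents. Separately, and whichever source is used, the missing cut-off at next therapy lets in neutropenia from other drugs. The definition also gives the observation arm no reference date, because that arm has no last dose, although SAP 12 presents safety by arm.

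This concerns one descriptive safety display and does not affect the primary analysis. It is worth changing because the data for a better derivation are already scheduled at every follow-up visit.

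**What to change.** Amend SAP 12.3 as follows.

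- **Main derivation:** first central-laboratory neutrophil count below 1000/µL (grade 3 or higher in Protocol Table 4) at or after day 42 following the last dose, in subjects whose previous count was at least 1000/µL, up to the start of new anti-cancer therapy. The previous-count condition keeps new episodes apart from the separately defined prolonged neutropenia.
- **Arms:** report the ofatumumab arm only, or define a reference date for observation. The last observation visit, already used in the AE collection rule, is one candidate.
- **Supporting count:** show the AE-based number separately, labelled as SAE-only after day 60.
- **Footnote:** state that 3-monthly sampling can miss short episodes.

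The cost is SAP wording and one extra derivation on data already collected. The reported rate may be less favourable. If the dataset specifications already use laboratory counts, the source change only puts that in the SAP; the cut-off at next therapy, the arm rule and the labelling still need to be settled.

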### **Autoimmune Hematologic Complication Adverse Events**

A summary of all autoimmune hematologic complication adverse events and all serious autoimmune hematologic complication adverse events reported within 60 days after the last ofatumumab dose will also be provided.

A subject listing of all events will be provided.

### **Tumor Lysis Syndrome (TLS)**

Laboratory TLS, calculated using the following criteria will be summarized:

Metabolic Abnormality	Criteria for Laboratory TLS	Criteria for Clinical TLS
Hyperuricemia	Uric acid >8.0 mg/dl	
Hyperphosphatemia	Phosphorus >4.5 mg/dl	
Hyperkalemia	Potassium >6.0 mmol/l	Cardiac dysrhythmia or sudden death probably or definitely caused by hyperkalemia
Hypocalcemia	Corrected calcium <7.0 mg/dl or ionized calcium <1.12 mg/dl	Cardiac dysrhythmia, sudden death, seizure, neuromuscular irritability (tetany, paresthesias, muscle twitching, carpopedal spasm, Trousseau's sign, Chvostek's sign, laryngospasm, or bronchospasm), hypotension, or heart failure probably or definitely caused by hypocalcemia
Acute kidney injury	NA	Increase in serum Creatinine level of 0.3 mg/dl (or a single value >1.5x ULN) or the presence of oliguria, defined as an average urine output of <0.5 ml/kg/hr for 6 hours

In laboratory tumor lysis syndrome, two or more metabolic abnormalities must be present during the same 24-hour period within 3 days before the start of therapy or up to 7 days afterward. Clinical tumor lysis syndrome requires the presence of laboratory tumor lysis syndrome plus an increased creatinine level, seizures, cardiac dysrhythmia, or death.

The corrected calcium level in mg/dL = measured calcium level in mg/d + 0.8x (4 – albumin in g/dl).

Acute kidney injury is defined as an increase in the creatinine level of at least 0.3 mg/dL or a period of oliguria lasting 6 hours or more. By definition, if acute kidney injury is present, the subject has clinical tumor lysis syndrome.

A listing of subjects with TLS (reported as an adverse event and subjects with laboratory TLS) will be provided.

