3.1.3. Treatment Phase

Subjects randomized to treatment arm A will receive ofatumumab whereas subjects randomized to treatment arm B will receive no further treatment (i.e. observation only).

Arm A:

Ofatumumab:

- 300mg IV Week 1 followed by 1000mg IV on Week 2
- 1000mg IV (1 dose every 8 weeks for up to 2 years following the first 1000 mg dose)

OR

Arm B:

- No further treatment (observation and assessments as per arm A)

Disease status assessments to determine subject response or progression will be performed approximately every 8 weeks for up to 2 years for both arms according to NCI Criteria [Hallek, 2008] and will include:

- Physical examination including lymph node examination, spleen and liver measurement, and detection of constitutional symptoms
- Peripheral blood sample evaluation of complete blood count (CBC) and differential (expressed in % and absolutes)

Monitoring and treatment of potential Tumor Lysis Syndrome (TLS) during the first cycle will be performed as per oncology standard of care.

Patient Reported Outcome (PRO) measures (EORTC QLQ-C30, EORTC QLQ-CLL16, EQ-5D) will be administered for completion by subjects at baseline, at each treatment visit beginning with Visit 3, at last visit, and at follow-up visits. A Health Change Questionnaire will be administered for completion by the subjects at all post baseline visits, as per Section 6.5.6.

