5.1.1. Ofatumumab

The investigational medical product, ofatumumab, is a clear liquid concentrate for solution for infusion presented in glass vials. Ofatumumab will be infused intravenously on day 1 (300mg) and day 8 (1000mg) in the first cycle, followed by infusions of 1000mg every 2 months.

The ofatumumab infusions will be prepared in 1000 mL sterile, pyrogen free 0.9% NaCl to yield a 0.3 mg/mL and 1 mg/mL ofatumumab concentration for the first and subsequent infusions, respectively. Please refer to the SPM for instruction correct preparation of the investigational medical product.

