6.3. Laboratory Assessments

All the analyses will be performed by a central laboratory, except for the direct antiglobulin test (Coomb's test) that will be performed locally. A detailed description of the procedures for sampling, handling, storage, and shipment of the laboratory samples and all material such as test tubes and labels is provided in the SPM or by the central laboratory.

The protocol should be followed as closely as possible, but if as per local practice, a blood draw for hematology analysis prior to the visit date is required, it would be acceptable for hematology analysis, but the blood draw can be taken no more than 3 days ahead of the visit date. Blood draws performed by local laboratories (e.g. for quicker pre-dose response assessment) of protocol required lab assessments are acceptable, however, it is important that the sample for the central laboratory analysis is taken at the same time. The local laboratory results of absolute neutrophil count (ANC), platelet count, peripheral blood lymphocytes, and hemoglobin must also be entered into the eCRF, if these results are used to manage a treatment decision. Central laboratory

information will also be entered into the eCRF. Safety assessments, such as hematology not specified in the protocol, are allowed between visits, per investigator discretion and local practice.

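### The SAP's laboratory tumor lysis rule needs phosphorus, which the protocol panel omits, and its window closes on the nominal day of the first 1000 mg dose, so a low count says little about absence of TLS; clinical TLS is also defined in two incompatible ways

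*SAP*

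**What the plan says.** SAP 12.3 (Tumor Lysis Syndrome) lists four laboratory criteria: uric acid, phosphorus, potassium and calcium (corrected or ionized). The phosphorus criterion is "Phosphorus >4.5 mg/dl". For laboratory TLS, "two or more metabolic abnormalities must be present during the same 24-hour period", and that period must lie "within 3 days before the start of therapy or up to 7 days afterward". The section says that laboratory TLS will be summarized, and that subjects with TLS reported as an adverse event or by the laboratory rule will be listed.

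The data come from the protocol:

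- **Panel.** The biochemistry panel in Protocol 6.3.2 begins "sodium, potassium, chloride, bicarbonate, calcium, blood urea nitrogen (BUN), creatinine, uric acid, total bilirubin, alkaline phosphatase (ALP" and continues with AST, ALT, LDH, albumin and glucose. Phosphorus is absent.
- **Local results.** Protocol 6.3 states: "The local laboratory results of absolute neutrophil count (ANC), platelet count, peripheral blood lymphocytes, and hemoglobin must also be entered into the eCRF". This applies where those results guided a treatment decision. All four are blood counts.
- **Dosing.** Protocol 5.1.1 gives ofatumumab "on day 1 (300mg) and day 8 (1000mg) in the first cycle".
- **Monitoring.** Protocol 3.1.3 states: "Monitoring and treatment of potential Tumor Lysis Syndrome (TLS) during the first cycle will be performed as per oncology standard of care". It sets no laboratory schedule for this.
- **Visits.** Appendix 1 marks biochemistry at screening, Visit 1, Visit 2 (Week 2, within 3 days either way) and then from Visit 3 (Week 9).

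On clinical TLS, SAP 12.3 first requires laboratory TLS plus a further sign. It later adds: "By definition, if acute kidney injury is present, the subject has clinical tumor lysis syndrome".

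**The concern.** TLS is singled out for special attention in Protocol 6.4.6 and SAP 12.3. A derived count is informative only if its components are measured and the samples follow the exposures of interest. Here one of the four components has no required data source, although Protocol 6.4.6 itself names raised phosphate as a sign of TLS. The window ends as the first 1000 mg dose falls due, and no later sample is scheduled for weeks.

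The rule has no denominator of evaluable subjects. A subject with no usable sample is therefore counted in the same way as a subject who was tested and found normal. A small or zero count could be taken as reassurance about the first cycle when much of that cycle was not observed.

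The conflict over acute kidney injury is separate. Two programmers could derive clinical TLS differently, and each could point to the text.

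**Working it through.** The plan states no expected TLS rate or count, so there is no figure to reproduce. The check compares the rule with the data the protocol requires.

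**1. Criteria against the panel.** Uric acid, potassium and calcium are on the panel. So is albumin, which the corrected-calcium formula needs. Phosphorus is not on it.

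- Qualifying pairs among four criteria: 4 × 3 / 2 = 6.
- Pairs without phosphorus: 3 × 2 / 2 = 3 (uric acid with potassium, uric acid with calcium, potassium with calcium).
- Pairs not assessable on required data: 6 − 3 = 3.

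**2. Window against doses.** SAP 9.2.2 makes the start of therapy Day 1, so 7 days afterward is Day 8, the nominal day of the first 1000 mg dose. Visit 2 may take place on Days 5 to 11. Days 5 to 8 lie inside the window and Days 9 to 11 outside.

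**3. Scheduled chemistry that can count.**

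| Sample | In the window? | What it can show |
|---|---|---|
| Screening (up to 14 days before dosing) | Only if within 3 days of dosing | Pre-existing abnormality |
| Visit 1 | Yes | Treated as pre-dose where no time is recorded (SAP 9.3) |
| Visit 2, Days 5 to 8 | Yes | Effect of the 300 mg dose, if drawn before infusion |
| Visit 2, Days 9 to 11 | No | – |
| Visit 3, Week 9 | No | – |

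Week 9 is Day (9 − 1) × 7 + 1 = 57, which is 57 − 8 = 49 days after Day 8. Extending the window to 7 days after the Day 8 infusion (Day 15) adds no scheduled sample after that visit. It recovers only a Visit 2 sample drawn on Days 9 to 11, plus any unscheduled results. The sampling schedule limits the rule more than the window does.

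**4. Illustration of losing phosphorus.** The documents give no abnormality rates. Assume that each analyte is abnormal at a given sample with probability p, independently of the others.

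- Three criteria: P3 = 3p²(1 − p) + p³
- Four criteria: P4 = 6p²(1 − p)² + 4p³(1 − p) + p⁴

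| p (assumed) | P3 | P4 | P3 / P4 |
|---|---|---|---|
| 1% | 0.030% | 0.059% | 50% |
| 2% | 0.12% | 0.23% | 51% |
| 5% | 0.73% | 1.40% | 52% |
| 10% | 2.8% | 5.2% | 54% |

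If phosphorus were abnormal 3, 5 or 10 times as often as each of the others (p from 1% to 5%), the share kept would be about 25–26%, 17–18% or 9–10%. Abnormalities that occur together would change these shares, and if all four always moved together nothing would be lost. The table shows the direction and how wide the range is. It does not estimate the rule's sensitivity in this trial.

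**5. Clinical TLS.** One sentence makes laboratory TLS a necessary condition. The later sentence makes acute kidney injury sufficient, without repeating that condition or giving a window. A subject with a creatinine rise of 0.3 mg/dL and no laboratory TLS is not a case under the first sentence and is a case under the second.

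**The case against.** The strongest reply is that the laboratory rule is neither empty nor the only TLS output.

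- **Three criteria remain**, and any two of them qualify. The 3 days before therapy also let pre-existing abnormalities count, which raises the number. A reader might infer that the count must be close to zero by construction. The documents do not support that, because they give no abnormality rates.
- **Phosphorus may exist in the database.** Protocol 6.3 sets a minimum for local results and allows extra safety tests between visits. SAP 9.2.7 provides for local values at baseline. TLS is monitored by standard of care, and the procedures manual is not available here. It is therefore too strong to say that the phosphorus criterion can never be met. It is only not required.
- **The 1000 mg dose can fall inside the window** if Visit 2 is held on Days 5 to 7. No scheduled sample follows it there, however.
- **Adverse events are covered.** SAP 12.2 plans tables of all TLS and serious TLS adverse events up to 60 days after last dosing.
- **Practical weight is small.** The output lists for the 280-event and final analyses show TLS only as Listings 23.0201 and 23.0202, with no laboratory-TLS count table. Subjects enter in remission, while Protocol 6.4.6 names high tumor burden as a risk factor, so few cases might be expected under any rule.
- **Acute kidney injury is not just any creatinine rise.** The section gives thresholds for creatinine and for oliguria. The later sentence may have been meant to apply only within laboratory TLS.

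All of this stands and limits the point. It leaves three problems: required data cannot supply one criterion, evaluability is not reported, and the two clinical sentences disagree.

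**Conclusion.** The concern holds as a minor point about what the laboratory TLS summary can show. On protocol-required data, 3 of 6 qualifying pairs cannot be assessed, the window closes on the nominal day of the first 1000 mg dose, and no chemistry is scheduled between Visit 2 and Week 9. Sensitivity is low, by an amount that the documents do not allow to be estimated, so a low count must not be read as absence of TLS. The two statements on clinical TLS contradict each other and must be reconciled.

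This rests on three assumptions: start of therapy is Day 1, Visit 2 chemistry is drawn before the infusion, and no phosphorus data are collected beyond what the protocol requires. Unscheduled or local results, if entered, would make the shortfall smaller. The primary and inferential secondary efficacy analyses are unaffected.

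**What to change.** Change SAP 12.3 only:

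- (a) Anchor the analysis window to the actual date of each of the two first-cycle infusions, and include any unscheduled or local chemistry in the database. This must be written out, because SAP 9.2.9 otherwise confines unscheduled results to worst-case displays and listings.
- (b) Report how many subjects had a post-infusion sample in the window, preferably for each infusion. State that phosphorus is not on the protocol panel. Where samples are lacking, report the subject as not evaluable instead of as having no TLS.
- (c) Label the laboratory rule supportive to the TLS adverse-event tables already planned in SAP 12.2.
- (d) Reconcile the two clinical TLS sentences so that one definition is applied in the analysis.

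The cost is SAP wording and reprogramming one derived flag. No samples are added and no patient management changes. The downside is that the report must say that laboratory TLS was only partly evaluable. A longer window alone would gain little, so (b) matters most.
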